645 3) An Adverse Device Effect as defined in section 5.1.1, unless excluded from reporting
646 in section 5.2
647 4) A systemic adverse event occurring in association with a study procedure

648 All *reportable* Adverse Events—whether volunteered by the participant, discovered by study
649 personnel during questioning, or detected through physical examination, laboratory test, or other
650 means—will be reported on an adverse event form online. Each adverse event form is reviewed
651 by the Medical Monitor to verify the coding and the reporting that is required.

652 **5.1.3 Relationship of Adverse Event to Study Device**

653 The study investigator will assess the relationship of any adverse event to be related or unrelated
654 by determining if there is a reasonable possibility that the adverse event may have been caused by
655 the study device.

656 To ensure consistency of adverse event causality assessments, investigators should apply the
657 following general guideline when determining whether an adverse event is related:

658 Yes

659 There is a plausible temporal relationship between the onset of the adverse event and the study
660 intervention, and the adverse event cannot be readily explained by the participant's clinical state,
661 intercurrent illness, or concomitant therapies; and/or the adverse event follows a known pattern of
662 response to the study intervention; and/or the adverse event abates or resolves upon discontinuation
663 of the study intervention or dose reduction and, if applicable, reappears upon re-challenge.

664 No

665 Evidence exists that the adverse event has an etiology other than the study intervention (e.g.,
666 preexisting medical condition, underlying disease, intercurrent illness, or concomitant
667 medication); and/or the adverse event has no plausible temporal relationship to study intervention.

668 **5.1.4 Intensity of Adverse Event**

669 The intensity of an adverse event will be rated on a three point scale: (1) mild, (2) moderate, or (3)
670 severe. It is emphasized that the term severe is a measure of intensity: thus a severe adverse event
671 is not necessarily serious. For example, itching for several days may be rated as severe, but may
672 not be clinically serious.

673 • MILD: Usually transient, requires no special treatment, and does not interfere with the
674 participant's daily activities.

675 • MODERATE: Usually causes a low level of inconvenience or concern to the participant and

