676 may interfere with daily activities, but is usually ameliorated by simple therapeutic measures.

677 • SEVERE: Interrupts a participant's usual daily activities and generally requires systemic drug
678 therapy or other treatment.

679 **5.1.5 Coding of Adverse Events**

680 Adverse events will be coded using the MedDRA dictionary. The Medical Monitor will review
681 the investigator's assessment of causality and may agree or disagree. Both the investigator's and
682 Medical Monitor's assessments will be recorded. The Medical Monitor will have the final say in
683 determining the causality.

684 Adverse events considered related to the study device that continue after the participant's
685 discontinuation or completion of the study will be followed until their medical outcome is
686 determined or until no further change in the condition is expected.

687 **5.1.6 Outcome of Adverse Event**

688 The outcome of each reportable adverse event will be classified by the investigator as follows:

689 • COMPLETE RECOVERY/RESOLVED – The participant recovered from the AE/SAE
690 without sequelae. Record the AE/SAE stop date.

691 • RECOVERED/RESOLVED WITH SEQUELAE – The event persisted and had stabilized
692 without change in the event anticipated. Record the AE/SAE stop date.

693 • FATAL – A fatal outcome is defined as the SAE that resulted in death. Only the event that
694 was the cause of death should be reported as fatal. AEs/SAEs that were ongoing at the time of
695 death; however, were not the cause of death, will be recorded as “resolved” at the time of death.

696 • ONGOING – An ongoing AE/SAE is defined as the event was ongoing with an undetermined
697 outcome.

698 • An ongoing outcome for which further improvement or worsening is possible will
699 require follow-up by the site in order to determine the final outcome of the AE/SAE.

700 • An ongoing outcome that is medically stable (further change not expected) will be
701 documented as such and will not require additional follow-up.

702 • The outcome of an ongoing event at the time of death that was not the cause of death,
703 will be updated and recorded as “resolved” with the date of death recorded as the stop
704 date.

705 If any reported adverse events classified as UADEs are ongoing with further improvement or
706 worsening possible when a participant completes the study (or withdraws), the event will be

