357 In addition, the following will be tabulated by treatment group:

- 358 • For each MedDRA System Organ Class, percentage of participants with at least one
359 serious event
- 360 • Number of adverse events thought by investigator to be related to treatment

361 No formal statistical comparisons will be performed for reported adverse events.

362 **6.0 Additional Tabulations and Analyses**

363 The following will be tabulated according to treatment group:

- 364 • Baseline demographic and clinical characteristics
 - 365 ○ for overall cohort
 - 366 ○ for Phase 2 participants
- 367 • Visit completion rate for each visit (excluding death)
- 368 • Protocol deviations
- 369 • Number of reported device issues
- 370 • Treatment completion

371 In addition, to evaluate the potential contralateral effect, visual acuity, OCT measurements, and
372 treatment for DME in non-study eyes will be tabulated at primary outcome visit by the treatment
373 group assigned to the study eye. These outcomes will be analyzed and presented similarly to the

374 primary and secondary analyses as specified above for the study eyes, with the exception that no
375 imputation will be performed for missing data. If the study eye receives a treatment for DR or
376 DME, the last non-study eye measurement prior to the study eye treatment will be used for
377 analysis.

378 This pilot study is being conducted to determine whether the conduct of a pivotal trial has merit
379 based on an anatomic outcome and to provide information on outcome measures needed to
380 design a pivotal trial. If the results of this study support proceeding with a pivotal trial after
381 evaluation of all the data and discussion within DRCR, information from this study will
382 contribute to designing the pivotal trial. The standard deviation of the difference in visual acuity
383 will be used in the sample size calculation of the pivotal trial. Patient compliance (for example,
384 the proportion of enrolled participants that are randomized and the proportion of randomized
385 participants who comply with the use of the study device post-randomization) will also aid in the
386 design of the pivotal trial.

387 **7.0 OCT Angiography Ancillary Study**

388 At a subset of sites with OCT angiography capabilities, images will be taken at baseline and
389 primary outcome to explore whether there are changes in any features evident on OCT

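### The only planned tabulation by relatedness uses the investigator's causality call alone, although the protocol gives the Medical Monitor the final determination

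*SAP*

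**What the plan says.** Causality is assessed in two steps. Protocol 5.1.3 places the initial judgment at the site: "The study investigator will assess the relationship of any adverse event to be related or unrelated". Protocol 5.1.5 then has the Medical Monitor review that judgment, with freedom to disagree. Both assessments are kept, and on causality "The Medical Monitor will have the final say in" the determination.

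The analysis sections use only the first step. SAP 5.0 lists, by treatment group, "Number of adverse events thought by investigator to be related to treatment", and Protocol 7.9 has the same bullet. The other safety outputs do not classify events by cause:

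- all reportable events by MedDRA term and System Organ Class, by treatment group;
- the frequency of each ocular event on an at-least-once-per-eye basis, and of each systemic event on an at-least-once-per-participant basis;
- serious events, introduced by "For each MedDRA System Organ Class, percentage of participants with at least one" serious event;
- "Number of reported device issues", in SAP 6.0 and Protocol 7.15.

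The safety output is descriptive throughout: "No formal statistical comparisons will be performed for reported adverse events".

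**The concern.** The protocol sets up a central review with authority over causality, and the analysis then reports the assessment that this review can overrule. A programmer who follows SAP 5.0 literally will count an event that the Medical Monitor judged unrelated and omit one that the Medical Monitor judged related. Neither document says why the non-final assessment was chosen.

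Two features of this trial add weight. With 134 participants at about 40 sites, a site averages 134/40 ≈ 3.4 participants, so local judgments are spread thinly and central review is the natural means of making them consistent. The plan also names no safety outcome of special interest, so this bullet is the only place where a reader will see device-related events counted.

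A smaller, linked matter is the unit of counting. The bullet gives a number of events with no participant count, while the neighbouring summaries are per eye or per participant. Several related events reported for one participant would be indistinguishable from single events in several participants.

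At stake is whether the related-event count, which will probably be quoted in the report, agrees with the trial's own final view of causality.

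**Working it through.** The documents state no figure that can be reproduced here, so the check compares the text and then shows in simple form how the two counts can differ.

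**Side by side**

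| Question | Source | Answer |
|---|---|---|
| Who makes the initial call? | Protocol 5.1.3 | Investigator, related or unrelated |
| Who reviews it? | Protocol 5.1.5 | Medical Monitor, who may disagree |
| What is stored? | Protocol 5.1.5 | Both assessments |
| Whose call is final? | Protocol 5.1.5 | Medical Monitor |
| Whose call is tabulated? | Protocol 7.9, SAP 5.0 | Investigator only |
| Does any other output use relatedness? | Protocol 7.9 and 7.15, SAP 5.0 and 6.0 | None |

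The SAP does not depart from the protocol's statistical chapter. The mismatch lies between Protocol 5.1.5 and both analysis sections.

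**How the counts differ.** Within one arm, let

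- a = events that both assessors call related,
- b = events that the investigator calls related and the Medical Monitor unrelated,
- c = events that the investigator calls unrelated and the Medical Monitor related.

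Planned count = a + b. Count by final determination = a + c. Difference = b − c.

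The difference is zero when the assessors always agree (b = c = 0). It is also zero when b = c > 0, but the two counts then contain different events. The documents give no value for a, b or c.

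**Illustration only.** Assume a planned count of 2 to 5 related events in an arm, with one downgraded (b = 1, c = 0):

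- planned 5, final 4: change 1/5 = 20%;
- planned 2, final 1: change 1/2 = 50%.

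The absolute change is one event in both cases. On the participant scale, with 134/2 = 67 per arm, one participant is 1/67 = 1.5%.

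**Counting unit.** The ocular and systemic frequencies and the serious-event summary are each on an at-least-once or percentage-of-participants basis. The related-event bullet is the exception. The documents do not say how recurrences are recorded, so how far repeat events would inflate the count cannot be worked out.

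**The case against.** The strongest reply is that the bullet says exactly what it is. A count labelled as the investigator's view is not false because someone else holds another view, and Protocol 5.1.5 does not say which assessment the analysis must use. The investigator's call is kept on record and is overruled only where there is disagreement. The choice could be defended on masking grounds: Protocol 1.5 aims to keep investigators masked, while the Medical Monitor's masking status is not stated. This stands as a reason to show the investigator's call. It does not justify omitting the final one, and it is weaker after the 4-month visit, when participants are unmasked (Protocol 3.1.3).

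Three stronger readings are tempting, and the documents do not support them.

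- *That this is the only summary able to separate device effects from background diabetic eye disease.* It is not. The trial is randomized and sham-controlled, and all reportable events are tabulated by arm. That comparison needs no individual causality judgment, and an upgraded event still appears in it.
- *That the table would contradict safety reports already issued.* Protocol 5.4 does not say whose relatedness assessment triggers notification, and the sentence in Protocol 5.1.5 on following related events does not say who considers them related. A conflict is possible but cannot be shown from the text.
- *That the count will be wrong by 20% to 50%.* Those percentages come wholly from an assumed number of events and one assumed disagreement.

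The bullet is also one descriptive line in a pilot study. The Medical Monitor reviews every adverse event form (Protocol 5.1.2), and the DSMC reviews cumulative adverse event data (Protocol 5.6). This limits the importance of the point but does not remove the mismatch.

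**Conclusion.** The point holds as a narrow reporting mismatch. The only planned tabulation by relatedness rests on the investigator's assessment, while the protocol makes the Medical Monitor's assessment final and records both. The resulting error in each arm is b − c events. It cannot be sized from the documents and may be zero. The conclusion rests on the wording of Protocol 5.1.3, 5.1.5 and 7.9 and SAP 5.0 and 6.0, and on no numerical assumption.

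The consequence is confined to descriptive safety reporting. No event is lost from the by-arm listings, and the primary and secondary efficacy analyses are unaffected. It is worth correcting because the correction is cheap and the related-event count is likely to be few and closely read.

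**What to change.** In SAP 5.0, and correspondingly in Protocol 7.9, replace the bullet with a tabulation by treatment group of events judged related under the final (Medical Monitor) determination, with the investigator's assessment in an adjacent column. For each assessment give the number of events and the number and percentage of participants with at least one related event, in line with the at-least-once convention used for the other adverse event summaries.

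If the sponsor prefers to keep the investigator's call as the main presentation, the SAP should say why and still show the final determination beside it.

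The cost is a wording change in two sections and extra table columns. No new data are needed, because Protocol 5.1.5 already has both assessments recorded.
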